9.1.4 Dose prescription

Table 1 below summarises the recommended dose and fractionation options that can be used. Where a range of doses is provided, it is advised that the maximum dose that can be achieved whilst meeting the OAR planning constraints is prescribed.

| Metastasis site | Total Dose (Gy) | No. of Fractions | Dose/fraction (Gy) | Frequency | Maximum duration (days) |
|-----------------|-----------------|------------------|--------------------|-------------------|-------------------------|
| Lung | 54 | 3 | 18 | Alt daily | 14 |
| | 55-60 | 5 | 11-12 | Alt daily | 21 |
| | 60 | 8 | 7.5 | Alt daily | 21 |
| Adrenal | 30-36 | 3 | 10-12 | Daily or Alt days | 7 |
| Liver | 45-48 | 3 | 15-16 | Alt daily | 7 |
| | 50-60 | 5 | 10-12 | Daily or Alt days | 14 |
| Spine | 24-27 | 3 | 8-9 | Alt days | 7 |
| Bone | 30-40 | 3 | 10-13.3 | Alt days | 7 |
| Lymph node | 30-40 | 3 | 10-13.3 | Alt days | 7 |

9.1.5 Treatment scheduling and gaps

Treatment can start on any day of the week. Treatment is delivered as per table 1, above, for the maximum number of days the treatment should be delivered over dependent on the dose fractionation schedule being used.

9.1.6 Repeat SBRT

Only those patients allocated SBRT treatment at randomisation should be offered repeat SBRT treatment upon development of new extra-cranial lesions, where the total number of metastatic lesions over time since diagnosis of metastatic disease remains ≤ 3 , and the primary site and other sites previously treated with SBRT are under control. Suitability of new lesions for further SBRT will be based on the same criteria as at trial entry (visible, imaging defined targets suitable for SBRT, $\leq 6\text{cm}$ ($\leq 5\text{cm}$ for lung metastases)). Where multiple lesions are treated over the course of the trial, composite dose volume data must be assessed and all normal tissue dose constraints need to be met by the composite plan. Particular caution is required where isodose lines overlap serial organs. Any previous radiotherapy before trial entry should also be taken into account. 50% isodose lines for plans to individual lesions should not overlap. A period >3 months since the last SBRT treatment is required before commencing repeat SBRT.

Re-irradiation

Further SBRT treatment of lesions previously treated with SBRT either as part of the trial or prior to trial entry is not permitted in the CORE trial.

9.1.7 Radiotherapy Quality Assurance (QA)

The NCRI Radiotherapy Trials Quality Assurance (RTTQA) group will oversee the quality assurance of the SBRT within the trial to ensure the safety and consistency of radiotherapy delivery at participating sites. Prior to inclusion in the trial, individual centres will need to demonstrate they have robust procedures in place to ensure high quality plan RTTQA guidelines will be met. Thereafter case reviews will be in accordance with the RTTQA group guidelines (www.rtttrialsqa.org.uk).

9.2 Standard of care treatment

Standard of care (SOC) is at the discretion of the local oncologist and will be defined for each patient at trial entry. The SOC treatment specified at randomisation should be administered irrespective of what arm the patient is randomised to (with the exception that palliative radiotherapy would not be administered if the patient was randomised to SBRT+SOC). It may include any standard therapy that is clinically appropriate: chemotherapy (including maintenance where appropriate), biological therapy, endocrine therapy, palliative radiotherapy ($\text{BED}_{10} \leq 40$ i.e. equivalent to 30Gy in 10 fractions or less) or observation or any combination of these. As indicated in the eligibility criteria, patients for whom standard of care would be ablative therapy (e.g. surgery, RFA, cryoablation) are not eligible for CORE participation.

If allocated to SOC only group, SOC treatment may begin on the same day of randomisation or as soon as possible after randomisation. If allocated to SBRT+ SOC group, SBRT will precede SOC with the exception of endocrine therapy which may be initiated following randomisation and be given concurrently with the SBRT. All patients should commence SOC therapy within 4 weeks of SBRT finishing.

For patients where a change in endocrine therapy preceded trial entry (within 8 weeks of randomisation for prostate cancer patients and within 10 weeks of randomisation for breast cancer patients) it should be stated at trial entry whether endocrine therapy will be the only SOC treatment or whether palliative radiotherapy will also be offered (if known at this point).

9.2.1 Systemic therapy Chemotherapy

For patients allocated to SBRT+SOC, a minimum period of 2 weeks after the final fraction of SBRT is suggested before chemotherapy is recommenced.

Radiosensitizers

Bevacizumab and any other potential radiosensitizers should be stopped 4 weeks prior to the start of SBRT treatment. Pre-treatment radiosensitizers information will be captured prior to the start of SBRT treatment. The management of potential radiosensitizers should be in accordance with local SBRT guidelines.

Tyrosine Kinase Inhibitors (TKIs) Therapy

The use of TKI for NSCLC patients is not permitted during SBRT. Patients in the SBRT + SOC group will need to stop TKI treatment at least one day and up to one week prior to commencing SBRT. TKI treatment can recommence one day after the patient receives their last fraction. The stop date of the last TKI treatment will be captured prior to the start of SBRT treatment. Where applicable, date of TKI treatment is recommenced post SBRT will also be captured.

Endocrine therapy

For patients allocated to SBRT+SOC where SOC is endocrine therapy, endocrine therapy may be initiated following randomisation and can be given concurrently with the SBRT.

9.2.2 Palliative radiotherapy

Patients in whom palliative radiotherapy to the target lesion would be indicated as SOC (examples may include symptomatic bone metastases or asymptomatic vertebral metastases where treatment to prevent spinal cord compression is felt to be indicated) should be entered into the trial before palliative RT. If the patient is allocated to SBRT + SOC group, the patient will receive SBRT alone.

The following fractionation schemes are permitted: 8Gy/1fr, 10Gy/1fr (lung metastases only), 20Gy/5fr and 30Gy/10fr.

The use of alternative palliative fractionation schedules should be discussed prior to trial entry with the CI. Those in whom a higher dose of radiation is felt to be indicated as part of standard therapy are not appropriate for trial entry.

9.3 Supportive care guidelines

All medication considered necessary for the patients' welfare and which is not expected to interfere with the evaluation of the treatment may be given at the discretion of the investigator. Toxicity should be managed as per local guidelines and RCR guidance where available (<https://www.rcr.ac.uk/clinical-oncology/being-consultant/guidance-and-standards>).

9.4 Concomitant therapy

All medication considered necessary for the patients' welfare and which is not expected to interfere with the evaluation of the treatment may be given at the discretion of the investigator. Prescription and over-the-

counter medications that the patient takes from 30 days prior to randomisation until the end of treatment visit (within +/- 7 days of the last fraction of SBRT or within 6 weeks after randomisation for patients randomised to SOC only) should be recorded on the eCRF.

9.5 Non-permissible medications/therapies

Ablative therapy (e.g. surgery, RFA, cryoablation, SBRT) is not permissible as a standard of care option following randomisation for patients as part of the trial.

10 SAFETY REPORTING

10.1 Definitions

Adverse Event (AE)

An AE is any untoward medical occurrence in a patient administered a study treatment; the event does not necessarily have a causal relationship with the treatment.

For the purpose of this trial, any detrimental change in the patient's condition subsequent to the start of the trial (i.e. randomisation) and during the follow-up period should be considered as an AE.

Serious Adverse Event (SAE)

An SAE is any untoward medical occurrence that occurs after randomisation and within the following 90 days and:

- results in death,
- is life-threatening
- requires hospitalisation or prolongation of existing inpatients' hospitalisation
- results in persistent or significant disability or incapacity
- is a congenital anomaly or birth defect

In addition, any radiotherapy related grade ≥ 4 events occurring between 90 days after randomisation and 5 years after randomisation should be reported according to serious adverse event reporting timelines.

Important adverse events that are not immediately life-threatening or do not result in death or hospitalisation but may jeopardise the subject or may require intervention to prevent one of the other outcomes listed in the definition above, may also be considered serious.

Progression of the indicated disease and death due to progression of the indicated disease are not considered SAEs.

Pregnancy or aid in the conception of a child whilst participating in a trial is not itself considered an SAE but should be followed up for congenital anomalies or birth defects.

Serious Adverse Reaction (SAR)

A serious adverse reaction is an SAE that is suspected as having a causal relationship to trial treatment, which for the purposes of this trial will be SBRT, as assessed by the investigator responsible for the care of the patient. A suspected causal relationship is defined as possibly, probably or definitely related (see definitions of causality table).

10.2 Definitions of causality

| Relationship | Description |
|----------------|---|
| Unrelated | There is no evidence of any causal relationship with the trial treatment (SBRT) |
| Unlikely | There is little evidence to suggest there is a causal relationship (e.g. the event did not occur within a reasonable time after administration of the trial treatment). There is another reasonable explanation for the event (e.g. the patient's clinical condition, other concomitant treatment) |
| Possible | There is some evidence to suggest a causal relationship (e.g. because the event occurs within a reasonable time after administration of the trial treatment). However, the influence of other factors may have contributed to the event (e.g. the patient's clinical condition, other concomitant treatments) |
| Probable | There is evidence to suggest a causal relationship, and the influence of other factors is unlikely |
| Definitely | There is clear evidence to suggest a causal relationship, and other possible contributing factors can be ruled out |
| Not assessable | There is insufficient or incomplete evidence to make a clinical judgement of the causal relationship. |

Related Unexpected Serious Adverse Event

- An adverse event that meets the definition of serious and is assessed by the CI or nominative representative as: "Related" – that is, it resulted from administration of any of the research procedures, and
- "Unexpected" – that is, the type of event is not listed in the protocol as an expected occurrence (see Appendix A6) or, in the opinion of the Chief Investigator, is not expected.

10.3 Reporting Adverse Events to ICR-CTSU

For non-UK reporting requirements please see Appendix A7

Any toxicity, sign or symptom that occurs after trial randomisation which is not unequivocally due to progression of disease, should be considered an AE.

All AEs must be reported on the relevant toxicity, sign or symptom CRF.

- **Toxicity evaluation for patients randomised to SOC group**

The National Cancer Institute Common Terminology Criteria for Adverse Events (CTCAE) version 4 scoring system will be used for toxicity assessment for patients randomised to the SOC group.

- **Toxicity evaluation for patients randomised to SBRT+SOC group**

The National Cancer Institute Common Terminology Criteria for Adverse Events (CTCAE) version 4 and the Radiation Therapy Oncology Group (RTOG) Morbidity Scoring Criteria scoring system will be used for toxicity assessment for patients randomised to the SBRT+SOC group.

The severity of AEs should be graded according to the appropriate CTCAE/RTOG criteria. For each AE, the highest grade observed since the last visit should be reported.

Whenever one or more toxicity/sign/symptom corresponds to a disease or a well-defined syndrome only the main disease/syndrome should be reported.

10.4 Reporting of Serious Adverse Events to ICR-CTSU

Any SAE that occurs following randomisation and up to 90 days post randomisation must be reported. As detailed above, radiotherapy related SAEs occurring from 90 days post randomisation to 5 years post randomisation in patients receiving SBRT treatment should also be reported.

All SAEs should be reported to ICR-CTSU within 24 hours of the Principal Investigator (or designated representative) becoming aware of the event, by completing the CORE SAE form and faxing to:

The ICR-CTSU safety desk
[contact]**
For the attention of the CORE Trial team

As much information as possible, including the Principal Investigator's assessment of causality, must be reported to ICR-CTSU in the first instance. Additional follow up information should be reported as soon as it is available.

All SAE forms must be completed signed and dated by the Principal Investigator or designated representative.

The Site SAE log should be completed and the SAE form filed in the Site Investigator File.

10.5 Serious Adverse Events exempt from expedited reporting

The expected adverse events listed in Appendix A6 do not require reporting as SAEs to ICR-CTSU if grade ≤ 2 but should be reported using the appropriate CRF

10.6 Review of Serious Adverse Events

The Chief Investigator (or designated representative) will assess all SAEs reported as related to the study treatment, which for the purposes of this trial will be SBRT, for causality and expectedness (NB. The Chief Investigator cannot down-grade the Principal Investigator's assessment of causality).

SAEs assessed as having a causal relationship to study treatment (SBRT) and as being unexpected will undergo expedited reporting to the relevant authorities and all other interested parties by ICR-CTSU (see Figure 1).

Sites should respond as soon as possible to requests from the Chief Investigator or designated representative (via ICR-CTSU) for further information that may be required for final assessment of an SAE.

10.7 Expedited reporting of Related Unexpected SAEs

If an SAE is identified as being related and unexpected by the Chief Investigator it will be reported by ICR-CTSU to the main REC, the Sponsor and all other interested parties within 15 days of being notified of the event.

The Principal Investigators at all actively recruiting sites will be informed of any related unexpected SAEs occurring within the trial at appropriate intervals.

The collaborative group in each participating country will report related unexpected SAEs as per their local requirements to IECs and local investigators.

10.8 Follow up of Serious Adverse Events

SAEs should be followed up until clinical recovery is complete or until disease has stabilised. SAE outcomes should be reported to ICR-CTSU using the relevant section of the SAE form as soon as the Principal Investigator or designee becomes aware of the outcome.

[figure not shown]
10.9 Annual safety reporting

An annual progress report will be provided to the main REC by ICR-CTSU and copied to the Sponsor and the collaborative group in each participating country at the end of the reporting year. This will include data about related unexpected SAEs and whether any safety concerns have arisen during the reporting period.

10.10 Reporting pregnancies

If any trial participant or a trial participants' partner becomes pregnant while receiving trial treatment (SBRT) or up to 90 days after receiving trial treatment, this should be reported to ICR-CTSU using the pregnancy reporting form. Participants who become pregnant should discontinue from trial treatment immediately. Pregnancies should be followed up until conclusion and all follow-up information should be reported to ICR-CTSU. If the outcome of the pregnancy meets the definition of serious (i.e. congenital abnormality) this should be reported to ICR-CTSU following the serious adverse event reporting procedures described above.

Figure 1: Flow diagram for SAE reporting, and action following report

NB. All SAEs should continue to be followed up as specified above

11 STATISTICAL CONSIDERATIONS

11.1 Statistical design and sample size justification

11.1.1 Statistical design

CORE is a phase II/III, multi-centre, non-blinded, parallel group randomised controlled trial in patients with breast, prostate or NSCLC primary cancer. A randomised trial is the most appropriate design to address the research question and minimise potential sources of bias. Three tumour types are included in the trial as there is currently insufficient evidence to choose a single tumour site to investigate. Whilst the increased heterogeneity with this approach is acknowledged it was felt that this is the most pragmatic design for phase II. The decision to include NSCLC, breast and prostate cancer was made following wide consultation with clinicians across the UK, including the relevant Clinical Studies Groups and CTRad.

Delivery of SBRT in this setting is novel across the UK and an early assessment of patient recruitment and feasibility of delivery in a multi-centre setting is essential. Assuming feasibility of recruitment and deliverability of SBRT are confirmed, an efficacy signal will be sought after across the three tumour sites. Assessing efficacy overall rather than in individual sites at this stage will enable a positive signal to be identified more quickly and at present there is no strong biological rationale why SBRT would be effective for some tumour sites and not others.

If a positive signal is seen in the phase II then the intention is for CORE to expand to parallel phase III trials. Unless there are data to suggest that a phase III trial will not be feasible in a particular tumour type, separate phase III trials are planned for breast, NSCLC and prostate cancer patients. The design and primary endpoint for the phase III trial has not been fixed in advance; this will allow better estimates of treatment effect and the experience gained in the phase II part of the trial in terms of the deliverability of SBRT nationally to be taken into account in phase III. In addition, data collected during phase II on the secondary endpoints will be used to inform the design of the phase III and support power calculations and therefore, in any revised design, patients from the phase II part will not be included in the analysis of phase III endpoints. This approach will also provide an opportunity to refine the intervention technique prior to initiation of phase III on the basis of experience gained in phase II if required.

11.1.2 Sample size

This phase II screening study has been designed with a primary endpoint of PFS, and relaxed one-sided $\alpha=0.20$ and $\beta=0.20$ (13). The control arm PFS is estimated based on the expected contribution of each primary tumour site to the overall final sample size. Based on observed recruitment in the first year this is estimated at 75% prostate, 14% breast and 11% lung. Assuming a median PFS of 5 months for NSCLC, 12 months for breast and 18 months for prostate patients (14-22), it is estimated that the median PFS in the control group after randomisation will be 16 months. The phase II SABR-COMET trial targets a hazard ratio (HR) for OS of 0.6 (23). For CORE, a more conservative effect size has been chosen reflecting clinical opinion of what would constitute a PFS signal worthy of a phase III OS trial. In order to detect a HR of 0.75 for improvement of PFS i.e. extending the median cohort PFS by 4 months in the experimental arm with 80% power, a total of 230 patients are required (138 events). Assuming a 5% rate of patients lost to follow up at the point of data analysis, a total of 242 patients will be required (121 per treatment group). Dependent on observed rates of accrual this total may increase to a maximum of 270 to allow for each cohort to achieve a minimum of 50 patients. The sample size calculations, made using the *artsurv* command in Stata version 13, assume 50% recruited in both years 1 and 2 and 12 months of additional follow up.

The decision rule to proceed to phase III will be based on a 3 outcome design. An overall result significant at the 10% level would support continuation to phase III; significance between 10% and 20% would require supportive evidence from secondary endpoints with a particular emphasis on local tumour control and FFWMD. If the significance is >20% then the study will not progress to phase III unless there is clear

heterogeneity of outcomes between the 3 tumour subgroups supporting a signal in selected tumour sites in which case consideration would be given to progressing to an extended phase 2 evaluation for that tumour site alone.

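### Section 11.1.2 gives a 16-month control median that matches the weighted mean of the site medians (15.73), not the median of the mixed arm (about 14.7), and a 4-month gain that does not follow from HR 0.75 if PFS is exponential

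*Protocol*

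**What the plan says.** All the figures stand in one paragraph of the protocol, section 11.1.2.

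- Case mix: "this is estimated at 75% prostate, 14% breast and 11% lung".
- Site medians: "Assuming a median PFS of 5 months for NSCLC, 12 months for breast and 18 months for prostate patients".
- Pooled control figure: "it is estimated that the median PFS in the control group after randomisation will be 16 months".
- Target: "In order to detect a HR of 0.75 for improvement of PFS i.e. extending the median cohort PFS by 4 months".
- Size: "a total of 230 patients are required (138 events"), at one-sided alpha 0.20 and 80% power.
- Timing: the calculations "assume 50% recruited in both years 1 and 2 and 12 months of additional follow up".

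The paragraph names the Stata command used. It does not say how 16 was obtained, which PFS distribution was assumed, or what control survival was entered.

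**The concern.** Two stated design figures do not follow from the inputs beside them.

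First, the median of an arm that mixes three sites is the time at which the weighted survival curve reaches one half. It is not the weighted mean of the three medians. A small group with early events (NSCLC, median 5 months) is nearly exhausted by the time the pooled curve reaches 50%, so the pooled median falls below the average.

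Second, a hazard ratio and a gain in median months are offered as the same target. Under exponential PFS they are different targets.

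The 16 months is the only pooled control assumption in the protocol, and the gain is measured from it. Section 1.4 calls it important to establish control outcomes prospectively, and section 11.1.1 says phase II results will inform phase III. A pooled control median near 14.7 months would be what the plan's own site inputs predict, yet it would look like a shortfall against 16. A reader also cannot tell whether the effect judged worth pursuing is HR 0.75 or a 4-month gain.

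**Working it through.** **Inputs, all from section 11.1.2.** Shares 0.75, 0.14 and 0.11; medians 18, 12 and 5 months (prostate, breast, NSCLC); HR 0.75; one-sided alpha 0.20; power 80%; 230 patients allocated 1:1; accrual over 24 months, half in each year, then 12 months of follow-up. *Assumptions:* accrual uniform within each year; PFS exponential within site, with Weibull shapes 0.7 to 2 as the range; the same HR in every site.

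**1. Required events.** With z = 0.8416 for both alpha and power:
- Schoenfeld: 4(0.8416 + 0.8416)² / (ln 0.75)² = 136.9, so 137.
- Freedman: (0.8416 + 0.8416)² × (1.75/0.25)² = 138.8, so 139.

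The stated 138 is reproduced. It depends on HR, alpha and power, not on the median.

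**2. Where 16 fits.** 0.75×18 + 0.14×12 + 0.11×5 = 13.50 + 1.68 + 0.55 = 15.73, which rounds to 16.

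**3. Median of the mixed control arm.** Solve 0.75×0.5^(t/18) + 0.14×0.5^(t/12) + 0.11×0.5^(t/5) = 0.5.
- At t = 14.7: 0.426 + 0.060 + 0.014 = 0.500.
- At t = 16 the sum is 0.473, so more than half have already had an event.

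The median is 14.70 months, and 16 is about 9% higher (16/14.70 = 1.09).

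**4. Gain implied by HR 0.75.** For Weibull shape k, a common HR multiplies every time by 0.75^(−1/k). For k = 1 the factor is 1/0.75.
- Single 16-month exponential: 16/0.75 = 21.3, a gain of 5.3.
- Exponential mixture: 14.70/0.75 = 19.60, a gain of 4.9.
- Conversely, 16 to 20 months is HR 16/20 = 0.80 under exponential PFS. That needs 228 (Schoenfeld) to 230 (Freedman) events. With 138 events the power is Φ(½√138 × ln 1.25 − 0.8416) = Φ(0.469) = 68%.

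**5. Sensitivity to shape (site mixture, HR 0.75).**

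| Weibull shape | Control median | SBRT median | Gain |
|---|---|---|---|
| 0.7 | 14.65 | 22.1 | 7.4 |
| 1.0 | 14.70 | 19.60 | 4.9 |
| 1.2 | 14.78 | 18.8 | 4.0 |
| 1.5 | 14.96 | 18.1 | 3.2 |
| 2.0 | 15.3 | 17.7 | 2.4 |

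The control median hardly moves with shape. The gain moves a great deal.

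**6. Events from 230 patients at month 36.** The event probability is 1 minus the mean of S(t) for t from 12 to 36, averaged over the two arms.

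| Control v SBRT | Events | Power at HR 0.75 |
|---|---|---|
| Exponential mixture, HR 0.75 | 138.2 | 80.2% |
| Single exponential, 16 v 21.3 | 133.4 | 79.4% |
| Single exponential, 15.73 v 20.97 | 134.8 | 79.6% |
| Single exponential, 16 v 20 | 136.0 | 79.8% |
| Single Weibull, shape 1.15, median 16, HR 0.75 | 137.9 | 80.2% |

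The power column takes the events in each row and evaluates them at HR 0.75. The 16 v 20 row shows only the event yield of that pair of medians.

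**The case against.** The strongest reply is that nothing in the design depends on the 16 months. The 138 events follow from HR, alpha and power. The decision rule in section 11.1.2 uses significance levels, and section 11.2.4 stratifies the log-rank test and the Cox model by disease site. Phase III is planned as separate trials by tumour type, informed by observed data. The case mix and site medians are themselves estimates, and about 1.3 months is small beside their uncertainty. All of this stands, and it limits the point to reporting.

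A second reply is that no PFS distribution is stated, so 14.7, 19.6 and a gain of about 5 months are conditional. This stands for the gain: within-site Weibull shape 1.2 returns exactly 4.0 months. It does not rescue the control median, which stays at or below 15.3 for every shape from 0.7 to 2.

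From the 133.4 events under a single 16-month exponential, a reader might infer that 16 months and 138 events cannot both hold, that only the site mixture gives 138, or that the trial is underpowered. The documents support none of these. A 16-month median with a mildly rising hazard (shape about 1.15) gives 137.9 events from 230 patients, and the exponential 16 v 20 months gives 136.0. Power at HR 0.75 is within one point of 80% in every case in the step 6 table. Nor does the protocol say that the mixture was what was entered; the match at 138.2 is suggestive and no more.

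**Conclusion.** The point holds as a correction of two stated figures. The 16 months is not the median implied by the protocol's own case mix and site medians. That value is about 14.7 months with exponential PFS within site, and 14.65 to 15.3 over Weibull shapes 0.7 to 2. That 16 came from averaging is an inference from the arithmetic.

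The 4-month gain does not correspond to HR 0.75 under exponential PFS, where the gain is 5.3 months from 16 or 4.9 from the mixture. Taken as an exponential move from 16 to 20 months, it is a different target (HR 0.80) that 138 events would detect with about 68% power. The size of this second mismatch depends on the distribution, which the protocol does not state.

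The sample size is not in question: 230 patients and 138 events are consistent with HR 0.75 and 80% power.

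**What to change.** In section 11.1.2:

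1. Replace 16 months with the median of the three-site mixture (about 14.7 months, exponential within site), or keep 16 and label it a weighted average of site medians.
2. State the control survival and the distribution that were entered in the calculation. The sponsor should take these from its own record; they should not be inferred from the match at 138 events.
3. Keep HR 0.75 as the design target and restate the gain in median PFS so that it agrees with HR 0.75 under that distribution (about 5 months if exponential), with the assumption written beside it.

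The cost is a change of wording in one paragraph. The hazard ratio, alpha, power, 230 patients and 138 events stay as they are.

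### The sample size section gives two different target effects: HR 0.75 on a 16-month control median is a gain of about 5.3 months, not 4, and a 4-month gain is HR 0.80, for which 138 events give about 68% power

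*Protocol*

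**What the plan says.** Everything is in Protocol section 11.1.2 (Sample size). The expected site mix "this is estimated at 75% prostate, 14% breast and 11% lung", and the site medians assumed for control PFS are 18, 12 and 5 months for prostate, breast and NSCLC. From these, "it is estimated that the median PFS in the control group after randomisation will be 16 months".

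The target is then to "detect a HR of 0.75 for improvement of PFS i.e. extending the median cohort PFS by 4 months in the experimental arm". The section continues "with 80% power, a total of 230 patients are required (138 events"), at one-sided alpha 0.20 and beta 0.20. It justifies the effect size by clinical opinion on what PFS signal would warrant a phase III survival trial, and calls it more conservative than the HR of 0.6 for overall survival targeted by another phase II trial. No survival distribution is named.

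**The concern.** The section presents a hazard ratio of 0.75 and a 4-month gain in median as one effect. With a 16-month control median the usual conversion does not link them. It makes HR 0.75 a larger gain than 4 months, and 4 months a weaker hazard ratio than 0.75. The stated power can belong to only one of the two.

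This is the design target for the primary endpoint, and its justification is clinical judgement about the smallest signal worth pursuing. A reader cannot tell which quantity that judgement was about. If it was 4 months, the risk of missing that effect is well above the stated 20%. The decision rule in the same section stops progression when significance exceeds 20%, apart from an exception for clear heterogeneity between tumour sites. If it was HR 0.75, the benefit in months is understated.

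**Working it through.** **Inputs, all from section 11.1.2 (1:1 allocation from 11.1.3).** One-sided alpha 0.20 and beta 0.20, so both normal quantiles are 0.8416. HR 0.75, control median 16 months, stated gain 4 months, 138 events, 230 patients. Site mix 75/14/11% with control medians 18/12/5 months (prostate/breast/NSCLC). Accrual over 24 months, half in each year, plus 12 months of follow-up. One assumption is added because the protocol states none: exponential PFS, so that the ratio of medians is 1/HR.

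**1. Reproducing the stated events and power.**
- Schoenfeld: 4 × (0.8416 + 0.8416)² / (ln 0.75)² = 136.9, so 137 events.
- Freedman: (0.8416 + 0.8416)² × (1.75/0.25)² = 138.8, so 139 events.
- Power with 138 events: Φ(√138/2 × |ln 0.75| − 0.8416) = 80.2%.

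The stated 138 events and 80% power are therefore right for HR 0.75. A two-sided alpha of 0.20 would need 218 to 221 events, so that reading is ruled out.

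**2. What HR 0.75 means in months.** 16/0.75 = 21.3 months, and 21.3 − 16 = 5.3 months.

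**3. What 4 months means as a hazard ratio.** 16/(16 + 4) = 0.80.
- Power with 138 events: Φ(√138/2 × |ln 0.80| − 0.8416) = 68.0% (Freedman 67.9%).
- Events for 80% power: 4 × (0.8416 + 0.8416)² / (ln 0.80)² = 227.6, so 228 (Freedman 230). 228/138 = 1.65, or 65% more.

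**4. Can another reading reconcile the two?**

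| Reading | Control median (months) | Median at HR 0.75 (months) | Gain (months) |
|---|---|---|---|
| Exponential, 16 as stated | 16.0 | 21.3 | 5.3 |
| Rounding of 16 (15.5 to 16.5) | 15.5 to 16.5 | 20.7 to 22.0 | 5.2 to 5.5 |
| Weighted mean of site medians | 15.7 | 21.0 | 5.2 |
| Exponential mixture of the three sites | 14.7 | 19.6 | 4.9 |

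The weighted mean is 0.75 × 18 + 0.14 × 12 + 0.11 × 5 = 15.73, which is probably where the 16 comes from. The mixture medians solve 0.75 × 0.5^(t/18) + 0.14 × 0.5^(t/12) + 0.11 × 0.5^(t/5) = 0.5, with each site median divided by 0.75 for the SBRT arm. On the mixture, a 4-month gain is HR 14.7/18.7 = 0.786, for which 138 events give about 72% power.

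**5. Where 4 months would fit.** 12/0.75 = 16, a gain of exactly 4, so the figure matches a 12-month control median. With medians of 12 and 16 months and the stated accrual and follow-up, the average event probability is 0.680, and 138/0.680 = 203 patients. That is close to the 206 patients still given as the total required in section 11.2.2. An incomplete update from an earlier design is a plausible explanation, but it is inference and nothing above depends on it.

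**The case against.** The strongest reply is that the months figure does no work. The event count, the Cox and log-rank analyses and the decision rule all run on the hazard ratio or on significance levels. The effect size is introduced by comparison with another trial's hazard ratio, so HR 0.75 is the natural reading of what was chosen. On that view the stated 80% power is correct and the 4 months is a loose gloss. This stands in part. The 68% applies only if 4 months is the intended target, and no document shows that the 4 months was agreed separately from the hazard ratio.

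A second reply is that the protocol never states exponential survival. With exponential medians of 16 and 21.3 months, the stated accrual and follow-up yield about 133 events in 230 patients, not 138. A Weibull shape of 1.15 to 1.2 yields about 138 to 139 events and gains of 4.5 to 4.3 months; a shape of 1.29 makes the gain exactly 4, with about 142 events. It is fair that 5.3 months and HR 0.80 are conditional on constant hazards. But the three-site exponential mixture, built only from the protocol's own inputs, gives 138.2 events without any shape parameter, and its gain is 4.9 months. Nothing in the protocol points to a Weibull model.

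Third, 12 to 16 months is exactly a 4-month gain in the breast cohort. The sentence, however, speaks of the cohort median in the experimental arm directly after the overall control median of 16 months, so that reading is strained.

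**Conclusion.** The section is wrong as written: HR 0.75 and a 4-month gain are not the same effect on a 16-month control median. The design is correctly powered for HR 0.75, which corresponds to a gain of about 5.3 months (4.9 on the three-site mixture). For a gain of 4 months, power with 138 events is about 68% (about 72% on the mixture), so the chance of missing such an effect is about 32% (28%) rather than the stated 20%.

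The conversions assume exponential PFS, overall or within each site, with proportional hazards. Neither rounding nor any assumption stated in the protocol reconciles the two figures. Which one was intended cannot be settled from the document.

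**What to change.** Name one target in section 11.1.2 and state the survival distribution behind the conversion.

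- If the hazard ratio is the target, replace the 4 months with HR 0.75, a control median of 16 months going to about 21.3 months (a gain of 5.3).
- If 4 months is the agreed minimum signal, state HR 0.80 and the power available for it, about 68% with 138 events at one-sided alpha 0.20.

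If the mixture of sites is preferred as the model, quote its own medians (14.7 and 19.6 months) in place of 16.

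The cost is one sentence. Recruitment, event target, analysis and decision rule stay as they are. Either the stated target benefit becomes larger or the stated power becomes lower.
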